1.2 Name and Description of Investigational Product or Intervention

Wet-to-dry dressings, consisting of gauze and sterile saline, will serve as the control. Petrolatum and non-stick gauze will serve as the intervention. Petrolatum will be directly applied to the wound surface and then be covered with a non-stick gauze.

1.3 Non-Clinical and Clinical Study Findings

Potential Benefits

There is potential that patients who participate in this research trial will receive additional monitoring compared to patients who do not (as they are receiving follow up surveys), which could help with identifying infection sooner. Analyzing the efficacy of petrolatum with non-stick bandaging at resolving HS postoperative wounds and decreasing pain could help guide dermatologists' treatment of HS and

provide better outcomes for patients in the future, including those in this study that might pursue additional procedures in the future.

Risks

Risks of participation include distress in anticipation of post-operative wound management, pain and discomfort following the procedure and with dressing changes, and infection. However, these risks accompany normal clinical unroofing procedures. There is always a risk of confidentiality breaches, but we will be mindful and attempt to minimize this risk. Normal clinic protocol for post-operative pain management will be followed, which includes opioid and non-opioid analgesics depending on provider and patient preferences and needs. Pain with dressing changes can occur, especially with wet-to-dry dressings. Patients will be informed of this risk during their dressing change postoperatively and during their bandage training session with the nurse. Patients will be instructed to contact the clinic in the event that dressing changes are too painful so that additional pharmacotherapy can be prescribed and other wound management strategies discussed. Patients will be made aware of this risk so that they can opt out of the bandaging protocol if needed.

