1.4 Primary Objectives

Primary Outcome Measures:

- 1. Change in Wound QOL Survey Score Over Time
 - a. A validated Wound Quality of Life (QOL) Survey will be administered that focuses on patient-reported outcomes of level of wound pain, pain with dressing changes (application and removal), satisfaction with the bandaging, and ease of application of the bandaging, all

17 elements on a 0-4 scale. Total score ranges from 0 to 4 with higher scores indicating a worse outcome.

- Time Frame: Administered at 1, 2, 4 and 6 weeks post-surgery
- 2. Change in PUSH Score Over Time
 - a. The pressure ulcer scale for healing (PUSH) tool is a validated means of measuring wound healing over time, specifically wounds that heal via secondary intent, by taking into account things like wound size and wound exudate, among others. Scores range from 0-17 with higher scores indicating inferior wound healing.
 - Time Frame: Completed at 1, 2, 4 and 6 weeks post-surgery utilizing images submitted by patients
- 3. Change in Pain with Dressing Changes
 - a. The numeric rating scale (NRS) will be used, where patients will be asked to rate pain with dressing changes and general pain on a scale from 0-10 with higher scores indicating worse pain. This information will be collected in the patient survey that is sent post-operatively.
 - Time Frame: Collected at 1, 2, 4 and 6 weeks post-surgery

Secondary Objective

The PWAT will be an important secondary endpoint for evaluation and comparison with the primary endpoints. Other patient-reported outcomes including interference with daily activities/exercise, assistance needed with bandaging changes, bandage change difficulty, and likelihood to use this bandage type in the future will be assessed. Additionally, patient-reported wound healing will be recorded. This will include questions such as "To what degree is the wound healed?" with answers on a 10-point scale ranging from "completely healed, somewhat healed, not healed." Number of days to wound healing/resolution will be asked on all surveys 4 weeks and later. Patients will also be asked whether or not they believe their wound is showing signs of infection.

2 INVESTIGATIONAL PLAN (brief overview)

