2.1 Study Design

Type of design: Randomized Controlled Trial

This will be a randomized, blinded trial of two postoperative bandaging techniques: wet-to-dry dressings vs. petrolatum with non-stick bandaging (see **Table 1).** Primary outcomes will be tracked using the PWAT, PUSH tool, and Wound QOL Survey (described below). Screening will be performed during regularly scheduled clinic visits with the principal investigator. Informed consent will be signed by the subject. A physical exam will be performed to assure that HS lesions suitable for surgical deroofing are present. Once subjects are deemed appropriate for the study, on the day of surgery the surgical sites will be marked with a skin marker and documented by body location. The surgical deroofing or excision procedure will then be performed by the principal investigator.

Study Phases are as follows:

Phase 1 (Day 0): Screening and Enrollment – patient's surgical date

Phase 2 (Weeks 1–Wound closure): patient survey completion and wound monitoring

Phase 3: Data Analysis

On the day of enrollment (patient's surgical date), patient age, sex, race, smoking history, and immunomodulatory medication use will be recorded. Assessment of wound size will also be measured by the PI on the day of surgery. The surgical procedure will be completed as it normally wound if the patient were outside the study. After the PI leaves the room, the patient is randomized to their treatment group and given their wound bandaging supplies and detailed instructions regarding the study protocol.

Patients will be instructed to expect receipt of a virtual RedCap questionnaire via electronic mail 1week post operatively and 2-weeks postoperatively. Questionnaires will continue to be sent every 2 weeks until the wound has fully closed. Disposable rulers will be provided that will be placed beside the wound for scale and patients will be instructed how to measure their wounds. The photos will be depersonalized and examined by the PI. Objective wound assessment will be completed using two standardized assessment tools. Wound assessment will be completed with the validated photographic wound assessment (PWAT) tool and the photographs will also be used to score and track wounds using the validated pressure ulcer scale for healing (PUSH) tool.

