If at any point patients develop a wound complication or wound like to have their wound examined or checked, they will be given contact information for the research fellow to schedule a follow-up visit.

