3.6 Screen failure procedures

If a patient does not meet inclusion criteria at enrollment, normal clinical care will resume with no detriment to the patient.

4 STUDY EVALUATIONS AND MEASUREMENTS (how measurements will be made)

- List variables that will be abstracted from medical charts

Page **12** of **20**

Baseline demographics including age, sex, race, BMI, smoking history, among others will be recorded from the medical chart and verified with the patient on the day of enrollment.

- Describe baseline evaluation

Baseline evaluation will include identifying surgical site, evaluating if surgical site is optimal for study inclusion, assessment of patient's overall general health,

- Describe how measurements will be taken.

Patient's upload a photo of their wound with each online survey they complete, as well answers to questions such as pain with wound dressing changes on a scale 1-10. Wound measurements and wound characterization for the primary and secondary endpoints will then be completed at the conclusion of the study by the PI. Other questions and data will be inputted by patients directly on the survey for future statistical evaluation.

- Describe rating scales, tests, psychological tools, laboratory evaluations, etc.

The previously-described PUSH, Wound QOL, and NRS primary endpoints will all be recorded and extrapolated from the online surveys submitted by patients at scheduled intervals.

STATISTICAL CONSIDERATIONS

Our study is powered to detect an effect on our primary endpoints, pain and quality of life. Although we will use the Wound Quality of Life (QoL) survey for our main analysis, as it is more comprehensive and we think readers will find it more persuasive, we don't have direct data on what to expect. Rather, we do have a strong sense, from clinical experience, of what will happen with pain. Using the 0-10 numerical pain scale, we believe the non-stick dressing will reduce pain ratings by 1.3 points at the two-week checkup and estimate the historical SD at that visit is 1.4 units, implying a .93 SD reduction. We calculate we will need 28 patients per arm to achieve 80% power. We add 2 more to account for two planned covariates (pelvic area vs armpit, and initial wound size). Since we expect approximately 20% dropout, we will plan to recruit approximately 74 patients.

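### The unblinding rule can remove patients from the pain analysis because dressing changes hurt, although NRS and Wound QOL are scored by patients who know their dressing anyway

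*Combined protocol and SAP*

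**What the plan says.** The combined protocol and SAP deals with painful dressing changes in several places.

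- **Section 1.3, Risks.** It expects the problem to differ by arm: "Pain with dressing changes can occur, especially with wet-to-dry dressings". The route for such patients is: "Patients will be instructed to contact the clinic in the event that dressing changes are too painful so that additional pharmacotherapy can be prescribed". It adds: "Patients will be made aware of this risk so that they can opt out of the bandaging protocol if needed".
- **Section 1.4, Primary Objectives.** Pain is a primary outcome, and "patients will be asked to rate pain with dressing changes and general pain on a scale from 0-10". The Wound QOL survey, also primary, is completed by the patient too.
- **Sections 2.2 and 6 (Blinding procedures).** The investigator is blinded; the patient is not, by design.
- **Section 7, Safety Management.** Patients with concerns may approach either the research fellow or the clinic. The text acknowledges that going to the clinic may compromise the investigator's blinding, and says that the investigator manages patients' wound-care needs.
- **Section 6, Unblinding procedures.** After unblinding, that patient's data are no longer usable for analysis. No endpoint is exempted.
- **Section 6, Subject Withdrawal.** Patients who cannot carry out the assigned wound care for a full week are withdrawn. It does not say what happens to scores they have already given.
- **Section 8.** A missed time point takes the previous value. Patients who do not return their surveys are left out of the analysis. Withdrawn patients are not mentioned.

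**The concern.** An exclusion that depends on what happens after randomization is harmless only if it is unrelated to outcome within arm. Here the event that starts the chain is pain at dressing changes, which is what the NRS measures, and the plan itself expects more of it in the control arm. If the patients in most pain are the ones who go to the clinic, become unblinded and are excluded, the wet-to-dry mean falls and the difference in favour of petrolatum shrinks. A small or null pain result would then be hard to interpret.

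The exclusion also brings no benefit on these endpoints. What the investigator knows cannot bias a score that the patient gives, and the patient knows the dressing from day 0. The 20% dropout allowance in Statistical Considerations replaces lost numbers; it does not correct a selective loss.

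**Working it through.** **Step 1: does the chain follow from the text?**

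| Link | Source | Strength |
|---|---|---|
| Dressing pain is expected more with wet-to-dry | 1.3, Risks | stated |
| Patient in too much pain contacts the clinic | 1.3, Risks | stated as an instruction |
| Clinic contact unblinds the investigator | 7 | possible, not certain |
| Unblinded patient's data leave the analysis | 6, Unblinding procedures | stated, all endpoints |
| Patient unable to do a week of assigned care is withdrawn | 6, Subject Withdrawal | stated; fate of earlier scores not stated |

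Only the third link is conditional. No rate is given for any of them.

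**Step 2: who scores what?** NRS and Wound QOL come from the patient. PUSH and PWAT are scored by the investigator from photographs (sections 2.1 and 4). The exclusion therefore has a rationale for PUSH and PWAT and none for NRS and Wound QOL.

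**Step 3: illustrative size.** Inputs from Statistical Considerations: expected difference 1.3 points at week 2; SD 1.4; 28 per arm plus 2 for covariates, read as 30 per arm. The plan's standardized effect reproduces: 1.3 / 1.4 = 0.93.

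Assume normal scores and that the k highest scorers of one arm of n are lost. The average fall in that arm's mean is

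shift = SD × (sum of the k largest expected normal order statistics) / (n − k).

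For n = 30 the three largest expected order statistics, by numerical integration, are 2.043, 1.616 and 1.365.

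- k = 1: 1.4 × 2.043 / 29 = 0.099
- k = 2: 1.4 × (2.043 + 1.616) / 28 = 0.183
- k = 3: 1.4 × (2.043 + 1.616 + 1.365) / 27 = 0.260

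As a share of 1.3 these are 7.6%, 14.1% and 20.0%. A simulation of 400,000 draws gave the same three shifts.

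**Step 4: sensitivity to n.** At 37 per arm (74 / 2, before dropout) the shifts are 0.083, 0.154 and 0.219. If the 2 added patients are a total and not per arm, n is (56 + 2) / 2 = 29, and the shifts are 0.101, 0.188 and 0.268.

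These are averages under normality, not bounds. They overstate the effect if those lost are not the very highest scorers. A single trial, or skewed scores, could exceed them. Losses of the same kind in the other arm would offset them.

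**The case against.** The strongest reply is that the chain is conditional. The patient must choose the clinic, although section 7 also offers the research fellow, and for a wound check section 2.1 says "they will be given contact information for the research fellow to schedule a follow-up visit". The investigator must then learn the dressing, and this must be treated as unblinding. All of that stands: it makes the frequency unknown, possibly zero. It does not make the rule harmless, because section 1.3 names the clinic, not the fellow, for painful changes.

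Second, the carry-forward rule in section 8 might keep a withdrawn patient's early, high score in the analysis, which is the opposite of selective loss. That is possible, but the text does not say whether the rule covers withdrawn patients. For unblinded patients, section 6 rules their data out.

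Third, a change to the analysis set now is late and could look post hoc. This is a fair cost, and the fix has to meet it.

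A reader might also infer something stronger: that analgesic use goes unrecorded, so the pain comparison is confounded and any difference in opioid exposure would stay hidden. Section 1.3 does leave analgesia open, "which includes opioid and non-opioid analgesics depending on provider and patient preferences and needs", and the only drug item named is in section 2.1: "patient age, sex, race, smoking history, and immunomodulatory medication use will be recorded". The documents still do not support that inference. The survey is not among them, and the data lists are open: "Other questions and data will be inputted by patients directly on the survey for future statistical evaluation". An analgesic item may exist. Comparing NRS under usual analgesia is also a valid comparison, and if rescue is commoner with wet-to-dry a positive result is, if anything, conservative. Nor is a large distortion likely. On an assumed drug effect of 1 to 2 points, halving the 1.3-point difference would need use in one arm to be 0.65 / 2 = 33 to 0.65 / 1 = 65 percentage points higher, beyond whatever the 1.3 already includes.

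**Conclusion.** The point holds for the exclusion rule. As written, section 6 allows patients to be removed after randomization for a reason linked to a primary outcome and expected to differ by arm, while protecting nothing on the two patient-scored primary endpoints. The likely direction is towards a smaller NRS difference, against the trial's own hypothesis.

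The size is unknown. For one to three losses among the highest scorers of 30, the average shift is about 0.10 to 0.26 points. That is enough to blur a modest difference, but not to erase one of the planned 1.3 points. The figures rest on normal scores, the plan's SD of 1.4, loss of the highest scorers, and loss in one arm only.

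It should not be concluded that contacting the clinic means exclusion, that anyone has in fact been excluded, or that the plan fails to collect analgesic data. The documents show none of these.

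**What to change.** Amend section 6 as follows.

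1. NRS and Wound QOL scores of patients whose allocation becomes known to the investigator are kept and analysed as randomized.
2. Scores already given by patients withdrawn for not completing a week of assigned care are also kept, with a statement of how the carry-forward rule in section 8 applies to them.
3. PUSH and PWAT are not covered by this change, because the investigator scores them.

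Section 2.3 gives actual enrolment as 74, and the synopsis dates end in October 2023, before the document date of 8/1/2024, so enrolment appears complete. The amendment should therefore be dated, and the analysis under the present exclusion reported as a sensitivity analysis, with the number of patients affected in each arm.

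The cost is a short change to the text and one extra analysis, with no added visits or patients. The downside is a documented late change to the analysis set.

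A minor option, not the correction of an error: a descriptive table by arm of analgesics prescribed, taken from the medical record under the separate authorization described in the consent text. No such report is described at present. At 30 per arm the 95% half-width for a difference is 1.96 × sqrt(2p(1 − p)/30), which is 15 percentage points at 10% use and 25 at 50%, so the table would show only large differences. It may also miss over-the-counter drugs.

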1.4 Relevant Literature and Data

Bandage Types

Wet-to-Dry Dressings

Wet-to-dry dressings have been the standard for wound care for many wound types for decades, including HS surgical wounds. This dressing technique involves moistening a piece of gauze with normal saline or other cleansing solution, placing the moistened gauze on the wound, allowing the gauze to dry, and then removing and replacing the bandage regularly over a period of days to weeks. Removing the dried gauze acts as a mechanical debridement agent. However, this wound dressing technique presents multiple problems, including a painful dressing change experience for patients, increased bleeding, removal of healthy, viable tissue, and local tissue cooling [1], all of which can impair would healing. Given the fact that other wound bandaging options exist which minimize the aforementioned negative effects, it is imperative to explore whether an alternate wound care strategy would be beneficial for HS patients undergoing surgery.

Petrolatum & Non-stick bandaging

An alternate wound dressing approach is applying a thick layer of petrolatum to the wound once or twice daily to maintain a moist wound base. The petrolatum often feels soothing when applied and seems to minimize wound discomfort [2]. After placement of petrolatum, the wound is covered with nonadherent gauze and tape or another bordered dressing. This bandaging strategy prevents the dressing from sticking directly to a wound base and typically makes bandage changes less painful. Since pain is a major drawback of wet-to-dry dressings, minimizing this experience for HS surgical patients would be highly beneficial. Additionally, this dressing technique keeps the wound bed moist and minimizes wound cooling, which are essential to optimal wound healing [3].

Evaluation Tools

The primary endpoint measures are the Wound QOL score, PUSH, and NRS tools, with the PWAT being an important secondary endpoint.

Wound QOL Score:

The wound QOL score has been used in a variety of different studies to evaluate chronic wounds. Although we will use the Wound Quality of Life (QoL) survey for our main analysis, as it is more comprehensive and we think readers will find it more persuasive, we don't have direct data on what to expect. The minimal important difference (MID) in Wound-QoL-17 overall score was determined in a German sample of 227 patients with chronic wounds and was found to be approximately 0.5 [4]. This means that a decrease of the Wound-QoL-17 total score of 0.50 or more in a group of patients can be assumed to indicate patient-relevant change. The global score ranges from 0 (= no impairment) to 4 (= maximum impairment).

PUSH

The pressure ulcer scale for healing (PUSH) tool is a well-validated and accurate measure of healing for chronic wounds that heal by secondary intention [5]. However, it has not been used frequently by the principal investigator as a measure of wound healing. Given the principal investigator's unfamiliarity in the clinical variance of PUSH scores between patients, we plan to power for non-inferiority between the two wound bandaging techniques in terms of wound healing as opposed to superiority of one bandaging type over the other.

NRS

The numerical rating scale (NRS) for pain ranges from 0-10. From prior studies on the NRS, we know that the minimal clinically significant difference in pain on the scale is approximately 1.3 points [6].

PWAT

The photographic wound assessment tool (PWAT) has been used in a wide variety of studies to monitor chronic wounds [7]. While it is not a primary endpoint for which the study is powered, it will still be completed and analyzed as a secondary outcome of interest.

1 STUDY OBJECTIVES

The purpose of this study is to determine whether wet-to-dry dressings should truly be standard of care or whether an alternate form of wound dressings, such as petrolatum with non-stick bandaging, is at least equitable if not superior in effect, and associated with fewer drawbacks such as associated pain and time dedicated to dressing changes.

1.4 Primary Objectives

Primary Outcome Measures:

- 1. Change in Wound QOL Survey Score Over Time
 - a. A validated Wound Quality of Life (QOL) Survey will be administered that focuses on patient-reported outcomes of level of wound pain, pain with dressing changes (application and removal), satisfaction with the bandaging, and ease of application of the bandaging, all

17 elements on a 0-4 scale. Total score ranges from 0 to 4 with higher scores indicating a worse outcome.

- Time Frame: Administered at 1, 2, 4 and 6 weeks post-surgery
- 2. Change in PUSH Score Over Time
 - a. The pressure ulcer scale for healing (PUSH) tool is a validated means of measuring wound healing over time, specifically wounds that heal via secondary intent, by taking into account things like wound size and wound exudate, among others. Scores range from 0-17 with higher scores indicating inferior wound healing.
 - Time Frame: Completed at 1, 2, 4 and 6 weeks post-surgery utilizing images submitted by patients
- 3. Change in Pain with Dressing Changes
 - a. The numeric rating scale (NRS) will be used, where patients will be asked to rate pain with dressing changes and general pain on a scale from 0-10 with higher scores indicating worse pain. This information will be collected in the patient survey that is sent post-operatively.
 - Time Frame: Collected at 1, 2, 4 and 6 weeks post-surgery

Secondary Objective

The PWAT will be an important secondary endpoint for evaluation and comparison with the primary endpoints. Other patient-reported outcomes including interference with daily activities/exercise, assistance needed with bandaging changes, bandage change difficulty, and likelihood to use this bandage type in the future will be assessed. Additionally, patient-reported wound healing will be recorded. This will include questions such as "To what degree is the wound healed?" with answers on a 10-point scale ranging from "completely healed, somewhat healed, not healed." Number of days to wound healing/resolution will be asked on all surveys 4 weeks and later. Patients will also be asked whether or not they believe their wound is showing signs of infection.

2 INVESTIGATIONAL PLAN (brief overview)

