2.2 Allocation to Treatment Groups and Blinding

Following the surgical procedure, the principal investigator ([name]) will exit the exam room. The principal investigator will thus be blinded to the wound dressing technique as he will not be present for bandaging administration, but the patient will not be blinded as they themselves will be administering the bandaging at home. The research fellow will complete randomization via the RedCap randomization algorithm and inform the patient of their assigned group.

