6 STUDY INTERVENTION ADMINISTRATION

- Randomization procedures

A stratified block randomization will take place after the principal investigator has left the surgical room following surgery. Randomization will be performed by the research fellow. Each participant is assigned to a particular stratum based on wound size and location, two important covariates to control for in statistical analysis given these variables can impact the Wound QOL survey and other results significantly. After strata assignment, randomization is completed via a RedCap algorithm. A detailed outline of the randomization process and groups can be found in **Figure 1**.

- Blinding procedures

Following the surgical procedure, the principal investigator will exit the exam room. The principal investigator will thus be blinded to the wound dressing technique as he will not be present for bandaging administration, but the patient will not be blinded as they themselves will be administering the bandaging at home.

- Unblinding procedures

If at any point unblinding occurs, the involved patient will be notified that their further participation in the study is voluntary but their patient data can no longer be used for analysis. There is no penalty or direct harm anticipated to the patient because of unblinding. They can continue to bandage their wound as assigned during randomization or alternatively if desired.

- Premature Study Closure

If any of the groups are showing significantly worse outcomes with regard to changes in pain or days to surgical wound resolution before the end of the recruitment period, the study will be ended prematurely.

- Subject Withdrawal

If a subject fails to complete a their one-week postoperative survey or are unable to complete the assigned wound care for a full week, they will be withdrawn from the study. All subjects will have the option to withdraw from the study at any time that they wish.

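### Days to healing, a secondary outcome, is a day count from unblinded patients first asked at week 4; the masked photo scores already planned are not used to date healing

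*Combined protocol and SAP*

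**What the plan says.** The Secondary Objective paragraph under section 1.4, Primary Objectives, introduces the healing items with "Additionally, patient-reported wound healing will be recorded" and then states: "Number of days to wound healing/resolution will be asked on all surveys 4 weeks and later". The day count is therefore a survey item first asked at week 4. No definition of healed accompanies it, and no analysis of it is described.

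On masking, section 2.2 says "the patient will not be blinded as they themselves will be administering the bandaging at home", and of the investigator: "The principal investigator will thus be blinded to the wound dressing technique as he will not be present for bandaging administration".

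On photos, section 4 (Study Evaluations and Measurements) says "Patient's upload a photo of their wound with each online survey they complete". Section 2.1 has the photos depersonalized and then scored by the PI with PWAT and PUSH. Section 1.4 sets PUSH at weeks 1, 2, 4 and 6; PWAT has no separate timetable. Section 4 fixes when the scoring is done: "Wound measurements and wound characterization for the primary and secondary endpoints will then be completed at the conclusion of the study by the PI".

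On survey timing, section 2.1 says "Questionnaires will continue to be sent every 2 weeks until the wound has fully closed", whereas the synopsis and sections 1.4 and 3.3 give surveys at weeks 1, 2, 4 and 6. Section 3.3 allows later ones if needed.

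Under Premature Study Closure, section 6 names "significantly worse outcomes with regard to changes in pain or days to surgical wound resolution" as grounds for ending the study.

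**The concern.** A day count asked after the event depends on memory and on what the respondent regards as healed. Here the respondent also knows the assigned dressing. Section 1.3 says that pain at dressing changes occurs particularly with wet-to-dry dressings and that patients will be told of this risk at training, so different expectations in the two arms are plausible. If those expectations move the reported day, the arms can differ with no difference in the wounds, or a real delay on petrolatum can be hidden.

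This is the only time-to-healing measure in the plan, and it will be read beside the Aim 3 claim that healing on petrolatum is not inferior. A source that does not depend on the patient's recall is already being collected and scored.

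**Working it through.** The documents give no SD, effect size or power for days to healing, so there is no stated figure to reproduce. Three checks were made.

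**1. Recall gap at the first asking.** Surveys fall on days 7, 14, 28 and 42, then every 14 days to day 84. The day count is first asked on day 28. This check assumes that fixed surveys continue at least to the first one that asks the question.

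Gap = day first asked − day healed.

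| Healed on days | First asked on day | Gap (days) | Width of photo interval (days) |
|---|---|---|---|
| 1–7 | 28 | 28−7 to 28−1 = 21–27 | 7 |
| 8–14 | 28 | 28−14 to 28−8 = 14–20 | 7 |
| 15–28 | 28 | 28−28 to 28−15 = 0–13 | 14 |
| 29–42 | 42 | 42−42 to 42−29 = 0–13 | 14 |

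Later healing repeats the last row. Long recall is confined to wounds healed by day 14. For those wounds, photos at days 7 and 14 exist before the question is first put.

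**2. The two survey schedules side by side.** If questionnaires stop at closure (section 2.1), a wound closed on day 10 would be recorded as closed at week 2, and the week-4 question might never reach that patient. If surveys run to week 6 regardless (synopsis, sections 1.4 and 3.3), the patient is asked on day 28, 18 days after closure. So early healers have either no day count or a long-recalled one. Both cannot hold for the same patient.

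**3. Effect of differential reporting (illustration).**

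- Analysed number: 74 × (1 − 0.20) = 59.2, or about 29 per arm, using the planned enrolment and the expected dropout in the Statistical Considerations.
- Assumed, not in the documents: SD of 7, 10 or 20 days; a shift of 1, 3 or 5 days between arms in mean reporting error; a two-sided 5% t-test on days; no true difference; every wound healed.
- Noncentrality = (shift / SD) / √(2/29), with √(2/29) = 0.263 and 56 degrees of freedom.
- For a 3-day shift: SD 7 gives 0.429/0.263 = 1.63; SD 10 gives 0.300/0.263 = 1.14; SD 20 gives 0.150/0.263 = 0.57.

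False-positive rates:

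| Shift | SD 7 | SD 10 | SD 20 |
|---|---|---|---|
| 1 day | 8% | 7% | 5% |
| 3 days | 36% | 20% | 9% |
| 5 days | 76% | 46% | 15% |

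The rate is close to nominal for a 1-day shift and clearly above it for 3 days or more.

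**The case against.** The strongest reply is that this is one item among several openly labelled as patient-reported, and that the main healing conclusion is already masked. PUSH carries the non-inferiority claim and is scored from photos by the blinded PI, with PWAT as a second photo-based measure. This stands, and it confines the problem to the secondary outcome.

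Sections 2.4 and the synopsis also exclude patients who prefer a particular bandaging protocol. That weakens the bias mechanism but does not remove it, since expectations can form after assignment and training.

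The illustration rests on assumed SDs and shifts, and on a test that the plan does not specify. That is also true; it shows sensitivity and does not estimate the bias. For wounds healing after day 14, the recall gap (0–13 days) is no longer than the photo interval (14 days). There the gain is independence from the unblinded reporter, not precision.

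Three stronger readings are tempting and are not supported:

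- A reader might infer that the patient's own view of closure ends the surveys. No section says who judges closure. The research fellow has access to the data, responses are reviewed every 2 to 3 weeks, and in-person visits are possible.
- A reader might infer that the premature-closure rule runs on this patient item. Section 6 does not state the source of its days to resolution.
- A reader might infer that the masked scores could correct that rule. They could not as planned: section 4 places PI scoring at study end, and section 8 gives the PI no data before then.

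PI masking is also imperfect. Section 7 accepts that it may be compromised when a patient contacts the clinic.

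**Conclusion.** The point holds for the final analysis of days to healing. The outcome depends on unblinded patients' reports, first requested at week 4, while masked photo scores planned at weeks 1, 2, 4 and 6 are not used to date healing. Differential reporting could create or hide an arm difference. Its size cannot be established from the documents. Under the stated assumptions a 3-day shift gives false-positive rates from about 9% (SD 20) to 36% (SD 7). The primary PUSH result is not affected, and nothing here shows that bias will occur. The conflict over survey timing is a separate, textual matter and stands without any assumption.

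**What to change.** - Define healed as the first survey photo that the masked PI scores as closed, and state what reading counts as closed.
- Analyse time to healing by arm as interval-censored between the last available open photo and the first closed one, adjusted for wound size and location, which the plan already names as covariates.
- Keep the patient's day count as a supportive outcome.
- State either that photos after week 6 are scored in the same way, or that healing time is censored at week 6. PUSH timing is given only to week 6.
- Reconcile section 2.1 (questionnaires until closure) with the synopsis and sections 1.4 and 3.3 (surveys at weeks 1, 2, 4 and 6), so that it is clear whether patients who close before week 4 are asked the day count and photographed again.

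The cost is a definition and one further analysis, largely on photos and scores already planned. Scoring photos after week 6 would add some work. The downside is resolution: healing is known only to a 1-week interval up to day 14 and a 2-week interval after that. The change serves the final analysis and leaves the section 6 premature-closure rule as it is.
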